### 2.1.1.3 Last Contact Day

The last contact day for the 12-month analyses will be determined by screening the 12-month database and taking the maximum of any dates found post-randomization. If the maximum date is after the cut-off date for the 12-month analysis, use the cut-off day as the last contact day for the 12-month analysis.

The last contact day for the 24 months analyses corresponds to the last recorded date in the database (across all visit dates itself, all visit related assessment dates, other assessment dates, event dates (start and end), medication dates). It should be prior to or on the day of study completion and therefore dates of events which occur after study completion will not be considered.

### 2.1.1.4 Baseline

The baseline value is the last non-missing value prior to the randomization.

The baseline body weight should be taken as the last non-missing weight prior to randomization. It is anticipated that in some cases, *baseline body weight* may be missing. In such cases, when used to derive other variable (i.e. dose per body weight), *baseline body weight* will be taken from the next available visit on the *Vital signs* form. However, in summary statistics of vital signs data, missing baseline body weights will be treated as missing. The exact algorithm to derive *baseline body weight* is as follows: it is the *last* assessment of any evaluations done up to the date of randomization; if there is no such assessment, it will be the *first* assessment taken after the date of randomization.

The baseline height will be derived in a similar way as the baseline body weight. Subsequently, BMI will be calculated.

### 2.1.1.5 On-Treatment

An *on-treatment* observation will be any assessment obtained on and after Day 1 but no later than two days after the discontinuation of randomized study medication. However, for AE/Infection, notable events, CMV information, EBV information and other events of interest, events occurring up to seven days (inclusive) after discontinuation of study medication are considered “*on-treatment*”.

## 2.2 Analysis Sets

The **full analysis set** (FAS) consists of all randomized and transplanted patients. Patients randomized but not transplanted will be excluded from the FAS. Patients who are mis-randomized due to documented (IVRS) administrative error (eligibility criteria) and have no study drug received are excluded from the FAS. Following the intention-to-treat (ITT) principle, patients will be analyzed according to their randomized treatment assignment and according to the actual stratum they initially belong to.

The **compliance set** (CS) consists of all patients in the FAS who are compliant for both CNI and investigational drug (EVR/MPA). Compliance is defined in [Section 2.4.2](#).

The **per-protocol set** (PPS) consists of all patients in the FAS who complete the study without any major deviations from protocol procedures. Major deviations include:

- Patient received multiple solid organ or tissue transplants (PD ID: EXCL04)
- Renal cold ischemia time > 30 hr (PD ID: INCL04)
- Patient received kidney from a non-heart beating donor (PD ID: INCL06)
- Patient Stratified incorrectly (PD ID: TRT08)
- Patient randomized but did not receive study drug (EVR or MPA) (PD ID: TRT01)
- Patient received treatment other than what they were randomized to (PD ID: TRT07)
- Induction agent other than basiliximab or rATG used (PD ID: TRT05)
- Patient did not receive any basiliximab or rATG for induction use (PD ID: TRT06)
- Prohibited Concomitant Medication used (PD ID: COMD03)
- Prednisone or equivalent was not used during the study (PD ID: TRT14)

The **safety set (SAF)** consists of all patients who received at least one dose of study drug. Patients will be analyzed according to their actual treatment regimen and according to the actual stratum they initially belong to. All safety analyses will be performed on the SAF.

Patients who did not sign the study main informed consent form will be excluded from any analysis sets (FAS, PPS, CS, and SAF). If a patient was mis-randomized due to documented (IVRS) administrative error (eligibility criteria), but received study drug, this patient will belong to both FAS and SAF. [Table 2-1](#) illustrates the selection of patients for the FAS and SAF.

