Control regimen	Drug regimen used post-randomization as a comparator to evaluate comparative effects of the investigational drug (i.e. the combination of MPA and a CNI- either tacrolimus or cyclosporine)		
Enrollment	Point/time of subject entry into the study; the point at which informed consent must be obtained (i.e. prior to starting any of the procedures described in the protocol)		
Extension	Study period from Month 12 visit to completion of Month 24 visit regardless of treatment status (i.e. can be on or off randomized regimen)		
Investigational regimen	The investigational drug regimen tested in the study post-randomization (i.e. the combination of everolimus and a CNI- either tacrolimus or cyclosporine)		
Lost to follow-up	Those subjects whose status is unclear because they fail to appear for study visits without stating an intention to withdraw and cannot be contacted		
Subject Number	A number assigned to each subject who enrolls into the study		
Period	A distinct stage in the subjects' participation in the study, each period serves a purpose in the study as a whole		
Premature subject withdrawal	Point when the subject exits from the study prior to the planned completi of all assessments, synonymous with study discontinuation, not the sam as treatment discontinuation		
Primary Treatment Period	Study period from randomization to completion of Month 12 visit, regardless of treatment status (i.e. can be on or off randomized regimen)		
Screening period	Period from signing informed consent to successful completion of the transplant procedure		
Study Completion	Point at which the subject came in for a final evaluation visit at Month 24 or complete discontinuation from the study if prior to Month 24		
Study drug/ treatment	Any single drug or drug regimen administered to the subject as part of the required study procedures in any study period, includes everolimus, tacrolimus, cyclosporine, basiliximab, MPA and corticosteroids		
Treated biopsy proved acute rejection (tBPAR)	An acute rejection episode documented by histological evidence for which anti-rejection therapy (e.g. steroids, antibody or increase in study regimen immunosuppression) was given.		
Treatment discontinuation	Point when subject permanently stops taking study/investigational or control treatment drug/regimen for any reason, not the same as study discontinuation/premature subject withdrawal		

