Subjects who discontinue their study treatment regimen should NOT be considered withdrawn from the study. Such subjects should remain in the study, if possible, and receive standard of care immunosuppression, according to local practice, until completing the study at Month 24. See Table 6-1 for the required assessments of these subjects after discontinuation of study regimen.

The status of every randomized subject must be recorded on Month 12 and/or Month 24 Study Phase Completion CRFs as either completing or discontinuing from the respective study period, with reason for discontinuation.

Possible reasons for discontinuation from the study are:

- Technical problems
- Subject/Guardian Decision
- Lost to follow-up
- Death
- **Graft Loss**
- Study terminated by sponsor
- Pregnancy

Subjects may voluntarily withdraw from the study for any reason at any time. They may be considered withdrawn if they state an intention to withdraw, fail to return for visits, or become lost to follow-up for any other reason.

If premature withdrawal occurs for any reason, the investigator must make every effort to determine the primary reason for a subject's premature withdrawal from the study and record this information on the Study Phase Completion CRF at Month 12 and/or Month 24 as applicable.

For subjects who are lost to follow-up (i.e. those subjects whose status is unclear because they fail to appear for study visits without stating an intention to withdraw), the investigator must show "due diligence" by documenting in the source documents steps taken to contact the subject, e.g. dates of telephone calls, registered letters, etc.

Subjects who are prematurely withdrawn from the study will not be replaced.

5.5.10 **Emergency breaking of treatment assignment**

Not applicable.

Study completion and post-study treatment 5.5.11

Subject who successfully complete 24 months on treatment may be eligible to participate in a separate observational extension study for a further three years. Subjects who are prematurely withdrawn from the study should be treated according to local standard of c are per investigator's judgment.

The study will be complete and ready for final analysis when the last active subject has completed their Month 24 visit.

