6.4 Efficacy

Treated Biopsy Proven Acute Rejection (tBPAR)

A treated BPAR is any condition where the subject received anti-rejection treatment and was histologically diagnosed as acute rejection (according to the Banff 2009 criteria, Appendix 6). Renal biopsies will be collected for all cases of suspected acute rejection.

Kidney allograft biopsy

For all suspected rejection episodes, regardless of initiation of anti-rejection treatment, an allograft biopsy must be performed within 48 hrs. Biopsies will be read by the local pathologist according to the updated Banff 2009 criteria (Appendix 6). The results of the biopsy read by the local pathologist will be listed on the Kidney Allograft Biopsy CRF. The results will be used for subject management for acute rejection. The local pathologist will remain blinded to

treatment. Any biopsies performed according to local practice (e.g. not for cause) should also be recorded.

Graft Loss

The allograft will be presumed to be lost on the day the subject starts dialysis and is not able to subsequently be removed from dialysis. If the subject undergoes allograft nephrectomy prior to starting permanent dialysis, then the day of nephrectomy is the day of graft loss. The reason for graft loss will be recorded on the Graft Loss CRF. This will be reported on the M12 or M24 study completion CRF with Graft Loss as the reason for study discontinuation and on the appropriate Dosage Administration Record CRF(s) if death occurs while on randomized treatment. Graft loss is considered a Serious Adverse Event and should be reported on the Adverse Event CRF (as serious) and the SAE reported to the local Novartis Drug Safety and Epidemiology Department local Novartis Drug Safety and Epidemiology (DS&E) Department within 24 hr.

Death

In the event of subject death, the SAE leading to Death should be reported to Novartis DS&E within 24 hr. The events leading to the death should be entered on the Adverse Event CRF and the death should be indicated on the appropriate Dosage Administration Record CRF(s) (if death occurs while on randomized treatment) and on the Study Completion CRF.

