The per-protocol set (PPS) consists of all subjects in the FAS who complete the study without any major deviations from protocol procedures. Major deviations include:

- Subject had multiple transplants or has had previous transplants
- Renal cold ischemia time > 30 hr

Additional protocol deviations and final definition of the PPS will be made based on blinded examination of the data prior to the 12-month and 24-month database locks.

The safety set (SAF) consists of all subjects who received at least one dose of study drug. Subjects will be analyzed according to the treatment they actually received.

All safety analyses will be performed on the SAF. Generally safety analyses will use treatment emergent data (on-treatment analysis by including data up to 2 days after the discontinuation of study drug). Selected variables will be analyzed using all available data including data assessed beyond study treatment discontinuation: AEs/infections and deaths.

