### **2.6.4 Supportive Analyses**

As supportive analyses, this non-inferiority analysis will be repeated using the Per-Protocol Set. Based on FAS, Kaplan-Meier event rates at Month 12 will be summarized for the subgroups defined in [Section 2.2.1](#).

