### 3 Determination of Sample Size

The sample size for this study was chosen with the goals to (1) have high power to evaluate non-inferiority in both the overall population *and* the TAC alone population and (2) have adequate power to evaluate superiority in the both the overall population *and* the TAC alone population.

With a sample size of n=1020 randomized per arm (EVR, MPA), the study has at least 95% power to demonstrate non-inferiority ( $\alpha=0.025$ , one-sided) in the overall and TAC alone populations at Month 12. There are at least 73% and 63% power ( $\alpha=0.025$ , one-sided) to demonstrate superiority of 7% or more in the overall and TAC alone populations, respectively.

The calculations are based on the following assumptions:

- 80% of patients are randomized to tacrolimus, 20% of patients are randomized to cyclosporine

- 20% and 30% patients are excluded from the PP population at Months 12 and 24 respectively
- For non-inferiority, the event rate in each arm is 50%, based on study results from RAD001A2309 and [Ekberg 2007](#), and the non-inferiority margin for the primary composite endpoint is 10%.
- For the evaluation of superiority, the event rate in the MPA + sCNI arm is 50%.

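### As worded, the per-protocol set drops patients who die or lose the graft, so the supportive per-protocol non-inferiority analyses select on their own endpoint events

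*SAP*

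**What the plan says.** SAP 2.2 defines the PPS as a set that "consists of all patients in the FAS who complete the study without any major deviations from protocol procedures", followed by a list of major deviations with identifiers. None of the listed deviations concerns death, graft loss or early termination. Protocol 9.1 carries the same completion condition with a shorter list, and adds that the "final definition of the PPS will be made based on blinded examination of the data" before each database lock.

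Protocol 5.5.9 requires every randomised patient to be recorded "as either completing or discontinuing from the respective study period", and lists death and graft loss among the reasons for discontinuing. Protocol 6.4 repeats this for graft loss: "This will be reported on the M12 or M24 study completion CRF with Graft Loss as the reason for study discontinuation". Stopping the study regimen, by contrast, is expressly not withdrawal from the study (5.5.9).

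The protocol glossary differs. Its entry for study completion covers the Month 24 visit "or complete discontinuation from the study if prior to Month 24".

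The PPS is used for supportive repeats of the primary analysis (SAP 2.5.4.2) and of the key secondary analysis, where "this non-inferiority analysis will be repeated using the Per-Protocol Set" (SAP 2.6.4). For planning, SAP 3 assumes that "20% and 30% patients are excluded from the PP population at Months 12 and 24 respectively".

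**The concern.** A per-protocol set is meant to select on adherence to the protocol. If completion is a condition and death and graft loss count as non-completion, this set also selects on outcome. A patient with a treated rejection and a surviving graft stays in. A patient who dies or loses the graft goes out, including one whose rejection led to that loss.

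For the key secondary endpoint, that removes two of the three components and leaves largely tBPAR. For the primary endpoint, it removes graft losses, which SAP 4.2.1.1 scores as eGFR 0 and hence as events. What is at stake is whether the PPS result can corroborate the FAS result. If the arms differ in graft loss or death, a PPS that omits those events cannot show it.

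**Working it through.** **1. The plan's own PPS figures.** Inputs from protocol 9.7 and SAP 3: 1020 per arm, event rate 50% in each arm, margin 10 points, one-sided alpha 0.025, PPS loss 20% at Month 12. PPS size = 1020 × 0.8 = 816 per arm. SE = √(2 × 0.5 × 0.5 / 816) = 0.0248. Power = Φ(0.10 / 0.0248 − 1.96) = 98.1%, against 98% in Table 9-1. The stated power is sound. The question is who is in the set.

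**2. Which reading applies.**
- Protocol 5.5.9 and 6.4: completing and discontinuing are alternatives, and death and graft loss are discontinuations. The PPS excludes these patients.
- Glossary: early discontinuation is itself a form of study completion. The condition then excludes nobody.
- No text exempts death or graft loss from the completion condition.
- The SAP does not say whether completion means Month 12 or Month 24, although the non-inferiority analyses are at Month 12.

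**3. Effect on the key secondary endpoint.** The documents give no death or graft-loss rates, so all rates here are assumptions. Let b be the tBPAR rate and q the rate of graft loss or death, taken as independent. FAS rate = 1 − (1 − b)(1 − q). Completers-only PPS rate = b. Differences are everolimus minus MPA, in percentage points.

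| b, EVR / MPA | q, EVR / MPA | FAS rates, EVR / MPA | FAS difference | PPS difference |
|---|---|---|---|---|
| 10% / 10% | 6% / 3% | 15.4% / 12.7% | +2.7 | 0 |
| 10% / 10% | 3% / 3% | 12.7% / 12.7% | 0 | 0 |
| 10% / 10% | 3% / 6% | 12.7% / 15.4% | −2.7 | 0 |
| 12% / 10% | 6% / 3% | 17.3% / 12.7% | +4.6 | +2.0 |

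First row: 1 − 0.90 × 0.94 = 0.154 and 1 − 0.90 × 0.97 = 0.127.

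**4. Stress case at the margin.** Suppose the true FAS difference is exactly 10 points, with MPA at b = 10% and q = 3% (FAS rate 12.7%). If 3 of the 10 points come from excess graft loss or death, everolimus has q = 6% and b = (0.227 − 0.06) / 0.94 = 17.8%. The PPS difference is 7.8 points. With 816 per arm, the chance that the PPS upper limit falls below 10 points is about 26%. It is 1.6% when none of the excess comes from those events, about 5% for 1 point, 12% for 2 and 68% for 5.

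**5. Effect on the primary endpoint.** Only graft loss acts here; a missing eGFR after death with a functioning graft is multiply imputed. With true rates of 60% and 50%, and graft loss of 2% on MPA, an excess of 3 points in graft loss gives a PPS pass probability of about 6%, against 2.1% with no excess.

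**The case against.** The strongest reply is that this touches no confirmatory conclusion. That stands: SAP 2.5.2 and 2.6.2 place both non-inferiority tests on the FAS, and no rule requires success in the PPS. A reader might infer that the PPS is a second required leg of the non-inferiority claim, or that type I error is at risk. The documents support neither.

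A reader might also infer that the exclusion always favours non-inferiority. It does so only if graft loss or death is more frequent on everolimus. With an excess on MPA, it removes an everolimus advantage. The prior evidence cited in protocol 3.6 reports similar patient and graft survival in study A2309, so the documents give no reason to expect a large imbalance either way.

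The illustrations in step 3 also change no decision. In the first row, the upper 95% limits are about 5.7 points (FAS, 1020 per arm) and 2.9 points (PPS, 816 per arm). In the last row, they are about 7.7 and 5.0. All are below 10.

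Finally, the wording may be inherited text and not a deliberate completers-only rule. A reader might take the planned rise in PPS loss from 20% to 30% as proof that non-completers are meant to go. It is suggestive at most: prohibited medication, treatment other than that randomised and absence of steroids can also accrue over time, and the protocol left further deviations open to blinded review. But that review has not removed the condition, which the current SAP still carries. If the glossary reading was intended, the condition has no effect and should go for that reason.

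**Conclusion.** The point holds as a defect in a supportive analysis set. Under the protocol's disposition rules, the PPS as written excludes patients for having graft loss or death. This matters most for the key secondary endpoint. For the primary endpoint it matters only through graft loss, and it would be wrong to describe that endpoint as containing death.

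The size cannot be fixed from the documents. Under the assumed rates, an imbalance of 3 points in graft loss or death moves the key secondary difference by about 2.7 points, in whichever direction the imbalance lies, and equal rates move it by about nil. These figures rest on independence of tBPAR from graft loss or death. The pass probabilities in steps 4 and 5 also rest on 816 patients per arm. The FAS results are untouched under every reading.

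**What to change.** In SAP 2.2 and protocol 9.1, delete the words 'who complete the study' and define the PPS as FAS patients without the listed major deviations. Add a sentence that death, graft loss and other early termination do not exclude a patient, and that such patients are analysed with their events, censoring or imputed eGFR as in the FAS. This also removes the conflict with the glossary and the question of which completion date counts.

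The cost is one phrase and one sentence, with no new data. The set becomes larger, but precision for the key secondary endpoint need not improve, because the restored patients are mostly events. In the first illustration, the standard error is √(2 × 0.10 × 0.90 / 816) = 1.49 points for completers only. Restoring the 6% and 3% gives 816 / 0.94 = 868 and 816 / 0.97 = 841 patients, and a standard error of √(0.154 × 0.846 / 868 + 0.127 × 0.873 / 841) = 1.68 points. That small loss is acceptable for an analysis that keeps its own endpoint.

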**Table 2-1 Selection of patients for the full-analysis set and the safety set**

IC	TX	RND	Mis-RND	RX	Dataset(s)
No	Y/N	Y/N	Y/N	Y/N	Exclusion
Yes	No	No	No	No	Screening failure
Yes	Yes	No	No	No	Randomization failure
Yes	Yes	Yes	No	Y/N	FAS
Yes	Yes	Yes	Yes	Yes	FAS
Yes	Y/N	Y/N	Y/N	Yes	SAF
Yes	No	Yes	Yes	No	Exclusion
Yes	Yes	Yes	Yes	No	Exclusion
Yes	No	Yes	No	No	Exclusion

IC=informed consent, Tx=transplantation, RND=randomization, Rx=study treatment

### 2.2.1 Subgroup of Interest

The following demographic/baseline characteristics are defined at the study level as subgroups for specified analyses:

- Recipient characteristics:
  - Age group: <60 vs ≥60 yr
  - Gender
  - Race: Caucasian, Black, Asian and All other races
  - Region: US, EU, Asia, Australia, Latin America, and Middle East

- DGF (delayed graft function)
- BMI <30 and  $\geq 30$
- Donor/transplant characteristics:
  - Age group: <60 vs  $\geq 60$  yr
  - Gender
  - Cold ischemia time: < 20 vs  $\geq 20$  hr
  - End stage disease leading to transplant (Glomerular disease, Diabetes mellitus and All other diseases)
  - Donor type (living donor, standard criteria and expanded criteria deceased donor): donor type will be derived based on Kidney Donor Background Information eCRF, and not the randomization stratification from IRT.
  - HLA mismatches:  $\leq 3$  vs  $> 3$
- CNI (tacrolimus vs. cyclosporine)
- Induction (basiliximab vs. rATG):
  - Basiliximab: preferred term: BASILIXIMAB; drug code/ID: 10892631
  - rATG: preferred term: ANTITHYMOCYTE IMMUNOGLOBULIN, or ANTITHYMOCYTE IMMUNOGLOBULIN (RABBIT); drug code/ID: 10878131 or 10878151

As early use of rATG can be for delayed graft function, type of induction will be identified as the first intake of rATG or basiliximab by Day 1 post-transplant.

## 2.3 Patient Disposition, Demographics and Baseline Characteristics

### 2.3.1 Patient Disposition

Patient disposition will be summarized in terms of the number and percentage of patients who complete the screening, prematurely discontinued from study medication and from study (by primary reasons). When there are multiple reasons for discontinuation associated to study drugs and CNI that happened the same day, the primary reason will be the one related to, by order of priority, Everolimus, Tacrolimus, MPA and Cyclosporine. The number of patients in the different analysis sets, incidence of protocol deviations, and incidence of major protocol deviations and other deviation criteria leading to exclusion from per-protocol set will be summarized by treatment group. Listings of screen failure and study completion with primary reasons for premature discontinuation of the randomized study treatment will also be provided.

In addition, the following listings will be presented:

- Screen failure
- Study completion status
- Protocol Deviations (PDs)
- Major protocol deviations and other deviation criteria leading to exclusion from per-protocol set
- Patients excluded from any analysis sets

